## 10.2 Randomization

This is a multicenter, randomized, double-blind, placebo controlled parallel group study. Subjects will be centrally randomized to one of 7 treatment sequences to receive lasmiditan 50 mg, lasmiditan 100 mg (L100 mg) or lasmiditan 200 mg (L200 mg) or placebo (P) for the first dose (in a 1:1:1:1 ratio) and the second dose for rescue or recurrence of migraine (if needed). Subjects will be stratified (yes or no) for use of concomitant medications that reduce the frequency of migraine episodes. Study drug will be randomized and dispensed at **Visit 1** as follows:

First dose for treatment of migraine	Second dose for rescue or recurrence of migraine (if needed)
L50 mg	L 50 mg
	L 50 mg
	placebo
L100 mg	L100 mg
	L100 mg
	placebo
L200 mg	L200 mg
	L200 mg
	placebo
placebo	placebo

## 10.3 Analysis Populations

### 10.3.1 Primary efficacy – FIRST dose

The statistical analysis of the first dose will be based on the analysis populations as defined below:

Safety population	All randomized subjects who use at least one dose of study drug, regardless of whether or not they undergo any study assessments. Subjects are evaluated by the drug they use, not by the drug to which they are randomized.
ITT population	All randomized subjects who use at least one dose of study drug and have any post-dose assessments. Subjects are evaluated by the drug to which they are randomized.
mITT population	All randomized subjects who use at least one dose of study drug to treat a qualifying migraine attack and have any post-dose assessments. Subjects are evaluated by the drug to which they are randomized.

**PP population** All ITT subjects will be considered per protocol (PP) if they dose a migraine attack and do not deviate from the protocol.

The following is a list of additional protocol violations which would exclude subjects from the PP population:

- Subject received excluded rescue medications or used rescue medication before 2 hour time point.
- Subject used recurrence medication before 2 hour time point.
- Subject did not receive study drug as assigned.
- Subject did not meet all inclusion/exclusion criteria.
- Subject did not treat a migraine of at least moderate severity.

### 10.3.2 Second Dose Analysis Populations

The analysis populations for the second dose used for rescue or for recurrence will be as defined below. Subjects **must** have taken the second dose and have been considered evaluable for the first dose and primary analysis to be included in the second dose analysis.

**Safety population** All randomized subjects who were considered in the safety population after the first dose and used a second dose of study drug, regardless of whether or not they undergo any study assessments. Subjects are evaluated by the drug they receive, not by the drug to which they are randomized.

**ITT-2nd Dose population** All randomized subjects who were considered ITT after the first dose and used a second dose of study drug and have any post-dose assessments. Subjects are evaluated by the drug to which they are randomized.

**mITT-2nd Dose population** All randomized subjects who were considered mITT after the first dose and used a second dose of study drug and have any post-second dose assessments. Subjects are evaluated by the drug to which they are randomized.

**PP-2nd Dose population** All ITT subjects will be considered per protocol (PP) if they use a second dose for rescue or recurrence of a migraine attack and do not deviate from the protocol.

The 2nd dose ITT, mITT and PP analysis populations will be further qualified by reason for second dose. Subjects will be considered in the 2nd dose rescue populations or 2nd dose recurrence populations as defined:

- **Rescue population:** All randomized subjects who did not achieve headache pain free at 2 hours, completed the 2 hour assessments and took a second dose of study drug between 2 hours and 24 hours.

- **Recurrence population:** All randomized subjects who achieved headache pain free at 2 hours, but then experienced recurrence of mild, moderate or severe migraine pain and took a second dose of study drug up to 24 hours from the first dose.

## 10.4 Accountability and Background Characteristics

### 10.4.1 Enrollment and Disposition

The number of subjects enrolled, by study population and Investigative site, will be presented by treatment. The primary reasons for discontinuation will be summarized by treatment and based on the safety population. The number and percentage of subjects with protocol deviations leading to exclusion from the PP population will be presented by reason for exclusion, stratified by treatment. All deviations will be listed.

### 10.4.2 Subject Characteristics

Subject characteristics will be obtained at the **Screening/Visit 1** prior to randomization and will be summarized by treatment and overall. Summaries will include descriptive statistics for continuous measures (sample size, mean, standard deviation, median, minimum, maximum) and for categorical measures (sample size, frequency and percentages). Treatments will be compared descriptively by using analysis of variance techniques for continuous data and Pearson's chi-square or Fisher's exact test for categorical data.

The results of these tests will be used in a descriptive way to highlight potential imbalances between the treatment groups. Subject characteristics may include, but are not limited to: age, gender, race/ethnicity, height, weight, BMI, and migraine history.

Subject characteristics will be summarized on all study populations.

### 10.4.3 Treatment Compliance

Treatment compliance will be assessed in terms of the actual dose. Treatment compliance will be used to characterize the patients and determine clinical evaluability for some analyses. Treatment compliance will be summarized within each treatment group by means of descriptive statistics (n, mean, SD, median, minimum and maximum).

## 10.5 Efficacy Analyses

All of the efficacy analyses will be performed on the ITT or mITT population. The primary analysis population is the mITT population. The PP population will be used as supportive analyses.

### 10.5.1 Primary Analysis

The treatment effect between lasmiditan and placebo will be tested first for the primary endpoint of the proportion of subjects who are headache pain free and the key secondary endpoint of the proportion of subjects who are MBS free at 2 hours in the mITT population between the lasmiditan 200 mg and placebo dose group based on the first dose. The primary analysis will be completed using logistic regression Wald Chi-square test with a basic model including treatment group and region, using a one-sided test at the  $\alpha=0.025$  level of significance.

If the primary analysis is statistically significant (one-sided,  $p<0.025$ ), additional confirmatory hypotheses will be tested on the proportion of subjects who are headache pain free and the proportion of subjects who are MBS free at 2 hours in the lasmiditan 100 mg and placebo

groups followed by the lasmiditan 50 mg and placebo groups.

Headache pain free at 2 hours will be defined as a reduction in headache severity from moderate (2) or severe (3) at baseline to none (0) two hours after dosing with study drug. MBS free at 2 hours will be defined as a 'no' response to the presence of the symptom (either nausea, phonophobia, or photophobia) that was identified as MBS at predose, 2 hours after dosing with study drug.

A qualifying migraine is defined as a migraine treated with study drug within 4 hours of onset.

Subjects taking rescue medication within the first two hours or who fail to record headache severity at 2 hours will be assumed to have no headache response in the mITT and the ITT analyses.

A subject is defined to have used rescue medication within the first two hours post dosing if at least one medication is documented in the rescue medication log in the subject electronic diary for which:

$0 \text{ (min)} < \text{date/ time rescue medication (diary)} - \text{date/ time of dosing (diary)} < 120 \text{ (min)}.$

Subjects who do not provide a headache pain severity rating at baseline or who use other medication prior to the study drug for the study migraine attack will be assumed to have no headache response for the ITT analysis.

#### **10.5.2 Sensitivity Analyses of the Primary and Key Secondary Endpoints**

The primary endpoint of pain free at 2 hours and the key secondary endpoint of MBS free are defined as proportions. The prespecified approach for handling missing data is to assume that subjects with missing data are nonresponders. While this approach is appropriately conservative, a sensitivity analysis will be incorporated to exclude subjects with missing data.

#### **10.5.3 Multiplicity Adjustment for Hypothesis Testing**

The gatekeeping procedure will be implemented to prevent Type I error inflation for multiple comparisons among the primary and secondary analyses. The treatment effect between lasmiditan 200 mg and placebo will be tested first for the primary endpoint of the proportion of subjects who are headache pain free and the key secondary endpoint of the proportion of subjects who are MBS free at 2 hours in the mITT population.

If the primary analysis is statistically significant (one-sided,  $p < 0.025$ ), additional confirmatory hypotheses will be tested in the mITT population in the following sequential order:

1. Proportion of subjects who are headache pain free at 2 hours in the lasmiditan 100 mg and placebo group.
2. Proportion of subjects who are MBS free at 2 hours in the lasmiditan 100 mg and placebo group.
3. Proportion of subjects who are headache pain free at 2 hours in the lasmiditan 50 mg and placebo group.
4. Proportion of subjects who are MBS free at 2 hours in the lasmiditan 50 mg and placebo group.

All of the above analyses will be completed using one-sided tests at the  $\alpha=0.025$  level of significance. If one of the analyses is not statistically significant, then all subsequent analyses will be exploratory rather than confirmatory.

#### **10.5.4 Other Efficacy Analyses**

##### **10.5.4.1 Headache relief**

The proportion of subjects with headache relief (moderate or severe headache at baseline, which became mild or none) at 2 hours post dose will be evaluated. The time course to headache relief will be explored up to 48 hours. Kaplan-Meier analysis will be performed to compare time course to headache relief between lasmiditan 200 mg and placebo, lasmiditan 100 mg and placebo and lasmiditan 50 mg and placebo.

##### **10.5.4.2 Headache recurrence**

The proportion of subjects with headache recurrence (moderate or severe headache at baseline, which became pain free at 2 hours post-dose and worsened again up to 48 hours post-dose) will be evaluated based on first dose. The frequency of recurrence will be compared by the same logistic regression model used for the primary endpoint analysis. The significance level of this exploratory analysis will be a nominal one-sided 0.05.

##### **10.5.4.3 Headache rescue**

The requirement for rescue medication at 2 hours and between 2 and 24 hours and 24- 8 hours (yes or no) will be evaluated based on first dose. The information on rescue medication use will be presented descriptively by time of use and treatment group.

##### **10.5.4.4 Associated Symptoms of Migraine**

Descriptive analysis of the associated symptoms of migraine, nausea, phonophobia and photophobia, will be performed at 2 hours. Freedom from each symptom will be defined as a 'no' response to the presence of the symptom 2 hours after dosing with study drug.

##### **10.5.4.5 Additional analyses**

Summary statistics will be presented on presence of vomiting, disability (4 point scale: not at all (0), mild interference (1), moderate interference (2), completely, needs bed rest (3)), and patient global impression of change (7 point scale).

#### **10.6 Analysis of Second dose**

All of the efficacy analyses will be performed on the ITT-2nd dose or mITT- 2nd dose population. The primary analysis population is the mITT-2nd dose population. The PP-2nd dose population will be used as supportive analyses.

##### **10.6.1 Analysis of second dose for rescue**

A second dose of study drug will be considered rescue medication if taken by a subject that did not achieve headache pain free at 2 hours and completed the 2 hour assessments prior to taking the second dose.

Summary statistics will be presented by treatment sequence on relief of migraine symptoms (pain free and MBS free) along with the time course to headache relief explored up to 48 hours. Subjects that use an alternative rescue medication will not be included in the summary statistics of response to treatment for rescue.

### **10.6.2 Analysis of second dose for recurrence**

A second dose of study drug will be considered treatment for recurrence if taken by a subject that achieved headache pain free at 2 hours, completed the 2 hour assessments, and then experienced documented recurrence of mild, moderate, or severe migraine pain prior to taking the second dose.

Summary statistics will be presented by treatment sequence on the relief of migraine symptoms (pain free and MBS free) along with the time course to headache relief explored up to 48 hours. Only subjects that used a second dose of study drug for recurrence of migraine will be included in the summary statistics of response to treatment for recurrence.

## **10.7 Missing Values**

The primary and key secondary endpoints are defined as proportions. If a subject has a missing value for a proportion endpoint, the subject will be classified as a nonresponder for this endpoint. Subjects who have more than one symptom (nausea, phonophobia or photophobia) but do not select one as the MBS prior to dosing, will be considered inevaluable for the MBS endpoint as there is no MBS selected to evaluate. In the case of subjects that have only one symptom (nausea, phonophobia, or photophobia) at predose but do not select a MBS, the one symptom will be considered the MBS for analysis.

For subjects who do not record a symptom rating, that symptom (pain, photophobia, phonophobia or nausea) will be assumed to be present at all time points where data are missing. Subjects who do not provide a headache severity rating at baseline will be assumed to have all four symptoms (pain, nausea, photophobia and phonophobia) at all time points. If recurrence medication is taken within 24 hours post dosing, or from 24 hours to 48 hours post dosing, even if no headache is reported, headache recurrence will be assumed for the first dose analysis.

The sensitivity analysis for handling missing data is described in detail in the SAP.

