### 9.1.8 Subject Diary

Subjects will be trained on the use of the electronic diary at **Screening/Visit 1**. Efficacy data will be collected in an electronic diary for an attack. Subjects will record the date and time at which their migraine headache starts and when it first becomes moderate or severe. They will also record the date and time of taking the first dose of study drug.

Subjects will be asked to assess their headache severity at specified time points: 0 (pre dose), 0.5, 1, 1.5, 2, 3, 4 and 24 and 48 hours post dose using the IHS four point headache severity rating scale (0 = no pain, 1 = mild pain, 2 = moderate pain, and 3 = severe pain). The need for rescue medication and second dosing of study drug or an alternative treatment will be assessed between 2 and 24 hour and at 48 hours. Recurrence of pain and second dosing of study drug will be assessed between 2 and 24 hours and at 48 hours.

At the same time points, 0 (pre dose), 0.5, 1, 1.5, 2, 3, 4, 24 and 48 hours, subjects will grade the degree of interference with normal activities and the presence or absence (yes or no) of accompanying symptoms: photophobia, phonophobia and nausea. At time 0 (pre dose) subjects will select from the accompanying symptoms present (nausea, phonophobia or photophobia) which one is the most bothersome to them. Subjects will be asked to record the presence or absence (yes or no) of vomiting. Subjects will also be asked to record the exact time at which headache relief became meaningful to them and the time at which they become headache pain free. At 2 hours subjects will be asked to record their global impression of change using a 7-point scale (very much better, much better, a little better, no change, a little worse, much worse, and very much worse).

The diary will also be used to record any symptoms or side effects the subject is experiencing and the use of any concomitant medications from **Visit 1** through to **EoS/Visit 2**

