 - The time intervals are 30 minutes, 1 hour, 1.5 hours, 2 hours, 3 hours, 4 hours, 24 hours, and 48 hours after the first dose of study medication. The e-diary sets the post dose assessments based on the recorded time of dosing. A subject that begins reporting their migraine at the exact time of dosing will have all of the post dose assessment time points available to them. If a subject starts recording their information in the e-diary after they dose including the time of dosing, the assessments that become available for them are based on the time of dosing, relative to when they accessed the e-diary. For example, if at 1-hour post actual dosing the subject initiates migraine mode and begins entering data into the e-diary, the subject will be allowed to respond to the initial questions about their migraine and time of dosing and then based on the time they record for dosing they automatically will miss subsequent time points, i.e.; the 30 minute and 1-hour time points. A missed time point is missed.
 - Alarms occur at the predefined time points to remind the subject it is time to complete the assessments. The Migraine Questions button is always available, but the subject is not be able to answer the questions until prompted by an alarm within a study migraine.
- Migraine Mode – Second Dose (Optional)
 - The subject should only take a second dose of study medication if the migraine pain is not gone by two hours after the first dose or the migraine pain was gone and came back two hours or more after the first dose (up to 24 hours after first dose).
 - The Dose 2 button will appear AFTER the e-diary recognizes 2 hours have passed since the first dose and remains until the 24-hour time point.
 - During the 2-hour post dose assessment the subject will be asked to indicate if he/she would like to take a second dose of study medication
 - If a second dose is reported alarm intervals are the same as for the reporting of the first dose and any remaining alarms from the first dose are cancelled. However, if

the subject inadvertently enters a dosing time of the second dose occurring prior to the first dose the first dose alarms do not stop and subject can therefore response to post-dose assessments based on time of dosing of first dose, therefore not really assessing their response to the second dose.

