5.3 Handling of Missing Values

Subjects who fail to record information at a particular analysis time point will have that value considered missing in the respective table, unless otherwise specified.

The primary and key secondary endpoints of headache severity and MBS presence at 2 hours post-dosing are two exceptions to this: (1) Subjects who fail to record a headache severity at 2 hours will be assumed to have not achieved headache pain-free, and (2) subjects who fail to record the absence of a symptom at 2 hours that was considered their MBS at baseline will be assumed to have not achieved MBS-free. A sensitivity analysis for missing data under alternative assumptions will be performed, as described in Section 11.5.

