11.7.11 Incidence of Headache Recurrence

The counts and percentages of subjects who experience headache recurrence will be presented by treatment group. The summary will be based on first dose using the ITT population.

A subject is defined to have experienced headache recurrence if they record a mild (1), moderate (2), or severe (3) headache at baseline which becomes pain-free at 2 hours post first dose and then becomes more severe up to 48 hours post first dose.

If the subject becomes pain-free at 2 hours post first dose and records the use of rescue medication, but no headache severity is recorded, it will be assumed that the medication is taken for recurrence, and the subject will be counted as having experienced headache recurrence.

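### Protocol and SAP score unrated 2-hour pain-free subjects in opposite directions for headache recurrence; the SAP rule under-counts, and the change is not declared

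*Protocol*

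**What the plan says.** **Protocol.** Section 10.5.4.2 counts as a recurrence a headache that was moderate or severe at baseline, "which became pain free at 2 hours post-dose and worsened again up to 48 hours post-dose". Section 9.1.8 schedules severity ratings at "0 (pre dose), 0.5, 1, 1.5, 2, 3, 4 and 24 and 48 hours post dose", so four ratings (3, 4, 24 and 48 hours) bear on recurrence. For a rating that is not recorded, section 10.7 says "that symptom (pain, photophobia, phonophobia or nausea) will be assumed to be present at all time points where data are missing". The sentence names pain and carries no restriction to the 2-hour or freedom endpoints. Section 10.7 then gives a recurrence rule of its own: if recurrence medication is taken within 48 hours, "even if no headache is reported, headache recurrence will be assumed for the first dose analysis".

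**SAP.** Section 5.3 sets the general rule: "Subjects who fail to record information at a particular analysis time point will have that value considered missing in the respective table", save where another rule is stated. The exceptions it names are the primary and key secondary endpoints at 2 hours. Section 11.7.11 counts a recurrence when a headache of any severity at baseline is one "which becomes pain-free at 2 hours post first dose and then becomes more severe up to 48 hours post first dose", or when a 2-hour pain-free subject records rescue medication and no severity. Section 5 makes the summarized population the default denominator for percentages; for recurrence this is ITT. On the diary, section 5 states "A missed time point is missed".

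**Disclosure.** Protocol section 10 requires changes of analysis method that do not need an amendment to be described and justified in the SAP. SAP 5.1 lists several changes, but not this one.

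**The concern.** Treating a blank as symptom present is the cautious choice for pain-free and MBS-free, where a blank then counts as failure. For recurrence the same assumption creates the event. The SAP goes the other way: a blank creates nothing, and the subject stays in the denominator as though followed and found free of recurrence. Neither rule separates subjects who did not recur from subjects who were not observed.

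At stake is an exploratory endpoint that Protocol 10.5.4.2 nonetheless compares between arms by logistic regression. A reader of the recurrence table cannot tell how much of the rate reflects incomplete diaries. A reader holding only the protocol would also assume a different rule from the one programmed. The missing-data sensitivity analyses in Protocol 10.5.2 and SAP 11.5 cover only the 2-hour primary and key secondary endpoints, so nothing planned addresses this.

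**Working it through.** **1. The same subject under each document.** Take a subject who is pain free at 2 hours, misses the 24-hour rating, records no pain at the other later ratings and takes no medication.
- Protocol: 10.7 assigns pain at 24 hours; 10.5.4.2 sees pain freedom at 2 hours followed by worsening. Result: recurrence.
- SAP: 5.3 leaves the rating missing; neither trigger in 11.7.11 is met. Unlike 11.7.3 and 11.7.5, section 11.7.11 does not drop subjects with missing ratings, so the default denominator keeps the subject in. Result: counted as not recurring. The SAP does not say so in words; it follows from the three sections together.
- Under SAP 11.7.2 this subject is not sustained pain-free at 24 hours either.

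**2. Size of the group at risk.** The pain-free rates are the sample-size inputs in Protocol 10.1. They reproduce the stated power above 90%: with 570 per arm and one-sided 0.025, a normal approximation for two proportions gives 94.6% (50 mg), 92.8% (100 mg) and 99.99% (200 mg). Expected 2-hour pain-free subjects per 570:
- placebo: 570 × 0.074 = 42
- 200 mg: 570 × 0.188 = 107

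The documents state no recurrence rate and no missed-rating rate. Everything below assumes a true recurrence rate r = 20% among 2-hour responders.

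**3. SAP rule (the planned table).** Let u be the share of responders whose later course is unobserved. Assume that recurrence is as common among them as among the rest, and that none of their recurrences is caught through medication. The reported rate is then r × (1 − u):
- u = 5%: 0.20 × 0.95 = 19%
- u = 20%: 0.20 × 0.80 = 16%

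Under equal recurrence these are floors, because recorded medication brings some cases back. The recurrences lost are r × u × responders: 0.4 to 1.7 subjects on placebo and 1.1 to 4.3 on 200 mg. On the ITT denominator, complete observation gives 0.20 × 7.4% = 1.5% and 0.20 × 18.8% = 3.8%. The SAP rule gives 1.2% to 1.4% and 3.0% to 3.6%.

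**4. Protocol rule (for contrast only).** Let m be the chance of missing each of the four later ratings, independently and with no medication use. The share missing at least one is 1 − (1 − m)^4, and the reported rate is r + (1 − r) × that share.

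| m | at least one missed | protocol rule, r = 20% |
|---|---|---|
| 2% | 7.8% | 26.2% |
| 5% | 18.5% | 34.8% |
| 10% | 34.4% | 47.5% |

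These figures show how far the two rules diverge. They do not predict the reported result.

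**The case against.** The best defence is that Protocol 10.7 was never meant to reach recurrence. The section opens with the primary and key secondary endpoints and ends with a separate recurrence rule based on medication. Assuming a symptom present assigns no severity grade, and section 10.6.2 speaks of documented recurrence. Section 9.1.8.2 also has the subject note when the headache returns, so recurrence is not captured only at scheduled prompts. This makes the intention doubtful, but does not change the text: the sentence covers all time points, the medication rule adds a trigger without cancelling the general one, any pain after none is a worsening, and 10.5.4.2 does not require documentation. SAP 11.7.11 does not say whether the noted time of return is used.

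The second defence largely stands. The SAP specifies the programmed analysis, and its recurrence rule is already close to the one recommended here. A reader might infer from the protocol rule that the table will show rates of 30% to 50%, or that 5% missed per rating on placebo against 10% on lasmiditan would yield a spurious odds ratio of about 1.69 (47.5% against 34.8%). The documents do not support that: the SAP will not produce those figures, the missingness rates are assumed, and the odds ratio is per responder whereas the SAP table is on ITT.

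A reader might also infer that missed ratings after 2 hours are built into the design, or more frequent on active drug because of somnolence. The diary has response windows and does not reopen missed points, but the SAP's example concerns late diary initiation and the loss of the 30-minute and 1-hour ratings. No passage predicts frequent misses after 2 hours or links them to sedation.

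Finally, sustained pain-free already treats an unrated 24- or 48-hour subject as a failure, which gives a rough worst case. It does not separate recurrence from non-observation, because medication use and missing ratings fall into the same remainder.

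**Conclusion.** The conflict is real and undeclared. For a 2-hour pain-free subject with a missed later rating and no medication, the protocol's text yields a recurrence and the SAP's yields none. Because the SAP governs the table, the practical consequence is under-counting of unobserved, unmedicated recurrences. The size cannot be established from the documents. The illustration of 16% to 19% against a true 20% of 2-hour responders rests on three assumptions: the 20%, an unobserved share of 5% to 20%, and equal recurrence in observed and unobserved subjects. If recurrence were commoner among the unobserved, the shortfall could be larger; recorded medication use makes it smaller.

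The direction of the disagreement depends on none of these assumptions. The endpoint is exploratory, tested at a nominal level and outside the gatekeeping sequence, so a reader should not infer any effect on the primary or key secondary conclusions.

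**What to change.** 1. In Protocol 10.7, confine the assumption that unrated symptoms are present to the freedom endpoints (pain-free, MBS-free, symptom-free and sustained pain-free).
2. In Protocol 10.5.4.2 and SAP 11.7.11, state that recurrence requires, after pain freedom at 2 hours, either a recorded return of pain or recorded use of rescue or recurrence medication.
3. In the recurrence table, add a row by arm, among 2-hour pain-free subjects, for those with no recorded recurrence who lack the 24-hour or 48-hour rating, labelled not assessed.
4. Add two bounds: all not-assessed subjects counted as not recurring, and all counted as recurring. With r = 20% and no capture through medication, the range would be 19% to 24% of responders if 5% are not assessed (19% + 5%), and 16% to 36% if 20% are (16% + 20%).
5. List the departure from the protocol, with its reason, in SAP 5.1. If the protocol is not otherwise being amended, its section 10 allows a change that is not a principal feature to be handled in the SAP and the study report.

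The cost is a sentence or two in each document, one table row and two bounding lines. No new data are needed. The drawback is that the recurrence estimate will appear with a visible unassessed group and, if many ratings are missing, a wide range.
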